### 3 STUDY DESIGN

#### 3.1 General Description

This single center, single-dose, randomized, adaptive, double-blind, placebo-controlled study will consist of 5 SAD cohorts. A total of 40 healthy, male and female nondependent, recreational polydrug users with opioid experience (8 subjects in each of the 5 cohorts) will be included.

Subjects will only participate in 1 cohort. The planned dose levels by cohort are presented in [Table 3-1](#).

**Table 3-1 Sample Dose Levels**

Cohort	Number of Subjects (active:placebo)	Dose a	Regimen
1	8 (6:2)	1 g (2 capsules)	
2	8 (6:2)	e.g., 2 g (4 capsules)	
3	8 (6:2)	e.g., 4 g (8 capsules)	
4	8 (6:2)	e.g., 6 g (12 capsules)	
5	8 (6:2)	e.g., 8 g (16 capsules)	Single oral administration of kratom or placebo on Day 1

a. Or until the maximum tolerated dose is defined

Dose levels presented are approximations and may be increased or decreased based on interim safety reviews. Doses may be increased, above those shown above in [Table 3-1](#), if there are no safety concerns and if it is deemed that there are minimal effects on PD measures. The upper dose may exceed 8 g if deemed appropriate and safe by interim data reviews.

Subjects will be confined to the clinical site from the day prior to drug administration until 48 hours following drug administration. Subjects will return to the clinical site for a Follow-Up Visit on Day  $7 \pm 2$ . The total duration of the study including Screening will be up to 37 days.

Blood samples for PK assessments will be collected before and over 48 hours after study drug administration. Assessments for the evaluation of PD will be performed before and over 24 hours after study drug administration. Safety and tolerability will be assessed throughout the study.

Following completion of each cohort, a Safety Review Committee (SRC) will review all safety and/or PD data to evaluate progression to the next dose cohort. The SRC will be comprised of the Principal Investigator at the Investigational site, the Study Manager and personnel from the Sponsor's scientific team at a minimum. Dosing of each cohort will be adequately scheduled apart to ensure sufficient time for review of the safety and PD data prior to dosing of the next cohort.

Subjects who terminate the study early will perform End of Study procedures (procedures from the Follow-Up Visit) as soon as possible after the time of Early Termination.

### **3.2 Treatments**

The following treatments will be administered in this study:

#### **3.2.1 Kratom 500 mg Capsules**

Kratom capsules consist of 500 mg kratom leaf powder filled into light blue gelatin capsules. Kratom 500 mg capsules are manufactured by Sun Distribution, Super Organics for oral administration.

#### **3.2.2 Placebo**

Placebo capsules made with microcrystalline cellulose will be matched to Kratom 500 mg Capsules. The weight will be matched to the Kratom 500 mg Capsules and the composition will be the same, including excipients.

### **3.3 Study Procedures**

For complete details on the study assessments to be performed for each study period, refer to [APPENDIX A](#).

#### **3.4 Randomization and Unblinding Procedures**

In each cohort, subjects will be randomized 6:2 (active: placebo). The clinical site will generate the randomization code with a computer program according to the study design, the number of subjects and the number of treatments. Once generated, the randomization code will be final and will not be modified.

The randomization code will not be available to the personnel of the bioanalytical facility until the bioanalytical phase of the study has been completed. The treatment assignment (active or placebo) will not be known by the study participants. Study participants will be informed of the dose range they could receive but will not be informed of the actual dose assigned to them.

Furthermore, the randomization code will not be available to the Investigator and clinical staff involved in the collection, monitoring, revision, or evaluation of AEs, as well as clinical staff who could have an impact on the outcome of the study including the pharmacokineticist (or

delegate) and biostatistician, until all the CRFs have been approved and signed and the bioanalytical phase of the study has been completed.

The preparation and/or administration of the products will be done by designated personnel who are not directly involved in the clinical aspects of the trial.

The randomization code must not be broken except in emergency situations where the identification of a subject's study treatment is required by an Investigator for further treatment to the subject or to complete a SAE report. Randomization information will be held by designated individual(s). The date and reason for breaking the blind must be recorded.

The results of the PD analyses will be made available only to the personnel responsible for evaluating the safety data before proceeding with the next dose level.

### **3.5 Determination of Sample Size**

No formal sample size analysis was performed. It is estimated that 8 subjects per cohort with 6 subjects assigned to the active drug and 2 subjects assigned to the placebo should be sufficient to meet the objectives of the study.

## **4 ANALYSIS POPULATIONS**

### **4.1 Randomized Population**

The Randomized population will include all subjects who are randomized to receive either active drug (kratom) or placebo in each cohort.

### **4.2 Safety Population**

The Safety population will include all subjects who received 1 dose of the active drug (kratom) or placebo.

### **4.3 Pharmacokinetic Population**

The PK population will include all subjects who have received at least 1 dose of the investigational product (IP) and have at least 1 mitragynine, 7-hydroxy-mitragynine, paynantheine, speciogynine, or speciociliatine postdose evaluable PK sample collected (based on viable PK samples).

Subjects who do not complete the blood sampling schedule may be included in the PK population for only the PK parameters that are judged not to be affected by the missing sample(s).

Subjects with protocol deviations or adverse events that could be considered to have an impact on the PK results may be excluded from the PK population. Participants who received only placebo will not be included in the PK population.

### **4.4 Completer Population**

All subjects in the Safety population who complete the dose level or placebo in their cohort, and have sufficient data for evaluation of the primary endpoint (based on a blinded review of data prior to database lock) will be included in the Completer population. Subjects who do not have at least 1 observation within 2 hours of  $T_{max}$  for Drug Liking VAS will be excluded from the Completer population.

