8.1.4. Completer Population

All subjects in the Safety population who complete the dose level or placebo in their cohort, and have sufficient data for evaluation of the primary endpoint (based on a blinded review of data prior to database lock) will be included in the Completer population. Subjects who do not have at least 1 observation within 2 hours of T_{max} for Drug Liking VAS will be excluded from the Completer population.

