### 8.4 Non-Compartmental Analysis

The following configuration for the NCA analysis (with Phoenix® WinNonlin® version 8.0, or higher) will be used:

- Data: Serial Sampled Data
- Model/Dose options Type: Plasma (200 -202) / Extravascular
- AUC Calculation Method: Linear-Up/Log-Down
- Lambda Z ( $\lambda_Z$ ) calculation: Best fit method for  $\lambda_Z$  Linear-Log regression

Reasons for excluding PK parameters will include the following:

- AUC: AUC parameters will not be estimated if less than 3 consecutive measurable concentrations are observed
- PK parameters requiring  $\lambda_Z$  estimation (eg,  $AUC_{0-\infty}$  and  $T_{\text{half}}$ ) will be set to Not Reported (NR) in the tables and listings if they meet one of the following:
  - $R^2 < 0.8$
  - The terminal half-life is higher than 2 times the time interval over which  $\lambda_Z$  is estimated (ie.  $T_{\text{half}} >$  twice the time interval difference between  $\lambda_Z$  Upper and  $\lambda_Z$  Lower).

The PK parameters for mitragynine, 7-hydroxy-mitragynine, paynantheine, speciogynine, and speciociliatine are defined in [Table 8-1](#).

**Table 8-1 Pharmacokinetic Parameters of Mitragynine, 7-Hydroxy-Mitragynine, Paynantheine, Speciogynine, and Speciociliatine in Plasma**

Parameter	Definition
$C_{\text{max}}$	Maximum observed concentration
$C_{\text{max}}/D$	Dose-normalized $C_{\text{max}}$ calculated at $C_{\text{max}} / \text{Dose}$
$T_{\text{max}}$	Time of maximum observed concentration; if it occurs at more than 1 timepoint, $T_{\text{max}}$ is defined as the first timepoint with this value
$AUC_{0-T}$	Area under the concentration time curve from time zero to the time of last quantifiable concentration ( $T_{\text{last}}$ )
$AUC_{0-T}/D$	Dose-normalized $AUC_{0-T}$ calculated as $AUC_{0-T} / \text{Dose}$
$AUC_{0-\infty}$	Area under the concentration time curve extrapolated to infinity, calculated as $AUC_{0-T} + C_{\text{last}}/\lambda_Z$ , where $C_{\text{last}}$ is the last quantifiable concentration at time $T_{\text{last}}$
$AUC_{0-\infty}/D$	Dose-normalized $AUC_{0-\infty}$ calculated as $AUC_{0-\infty} / \text{Dose}$
AUC%Extrap	Extrapolated area (ie, percentage of $AUC_{0-\infty}$ due to extrapolation from $T_{\text{last}}$ to infinity: $AUC_{0-\infty} - AUC_{0-T} / AUC_{0-\infty} * 100$ )
$\lambda_Z$	Apparent elimination rate constant, estimated by linear regression of the terminal linear portion of the log concentration versus time curve

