## 9 PHARMACODYNAMIC ANALYSIS

Unless otherwise specified, all available PD data and analysis results will be presented for the Completer population.

The PD measures at each time point will be summarized by treatment using descriptive statistics and presented graphically. Derived endpoints will be summarized by treatment and paired difference using descriptive statistics.

Descriptive statistics will include n, mean, standard error (SE), minimum, first quartile (Q1), median, third quartile (Q3) and maximum for all PD values and endpoints other than  $TE_{max}$  and  $TE_{min}$ . For  $TE_{max}$  and  $TE_{min}$ , minimum, Q1, median, Q3 and maximum will be presented.

Derivations for PD endpoints will be calculated as described below:

PD Endpoints	Definition
$E_{min}$	Minimum observed post-dose effect
$E_{max}$	Maximum observed post-dose effect
$TE_{min}$	Time of minimum observed post-dose effect
$TE_{max}$	Time of maximum observed post-dose effect
TA_AUE 	Time-averaged area under the effect-time curve (pre-dose - post-dose)
TA_AOE 	Time-averaged area over the effect-time curve (pre-dose - post-dose)

For time-averaged area over the effect-time-curve and area under the effect-time-curve (TA-AUE and TA\_AOE), will be calculated as the area over(or under) the curve relative to the baseline value divided by the time from time 0 to the X hour time point. TA\_AOE will be calculated using the linear trapezoidal rule applied to non-missing data. TA\_AOE will not be calculated if the first or last scheduled time point are missing. Assessments performed outside the assessment windows may be excluded from by-time point summary statistics; this will be determined prior to unblinding.

Derived Variable	Variables Used	Calculation	Comment

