### 9.3 Analysis of Pharmacodynamics Measures

The primary PD endpoint of this study is the maximum (peak) effect (Emax) over 24 hours for Drug Liking (“at this moment”), assessed on a bipolar (0 to 100 points) visual analog scale (VAS). This endpoint will be summarized with descriptive statistics. Placebo will be pooled across all cohorts.

$E_{max}$  as well as  $T_{max}$  and TA\_AUE of key secondary PD endpoints, Overall Drug Liking, Take Drug Again, and High VAS will be summarized similarly by treatment for the Completer population using descriptive statistics. All PD measures at each time point will be summarized by treatment using descriptive statistics and presented graphically. Derived endpoints will be summarized by treatment and paired difference using descriptive statistics.

A mixed-effects model will be used to compare PD endpoints between Kratom dose levels and placebo for all primary and secondary PD endpoints other than the 12-hour postdose results from Drug Similarity VAS and  $TE_{max}$  and  $TE_{min}$  endpoints. The model will include dose level as a fixed effect and the baseline score as a covariate [where applicable]. P-values for key components of variance, least-square means (LSmeans), and 95% CI for contrasts will be output for each pairwise comparison for Kratom dose levels versus placebo.

For each PD endpoint, the following comparison will be made:

- Kratom 1 g vs. Placebo
- Kratom 2 g vs. Placebo
- Kratom 4 g vs. Placebo
- Kratom 6 g vs. Placebo
- Kratom 8 g vs. Placebo

The Hodges-Lehmann estimate of the location shift, the asymptotic confidence limits, and the asymptotic standard error estimate will be used to estimate the 95% CIs of  $TE_{max}$  and  $TE_{min}$  secondary endpoints between the Kratom dose levels and placebo. The asymptotic standard error estimate is based on the length of the CIs. Rank sums and p-values from the Wilcoxon Rank Sum test will also be output.

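### Does the undefined Tmax in the Completer rule leave the pharmacodynamic analysis set unworkable?

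*SAP*

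**What the plan says.** SAP 4.4 builds the Completer population from the Safety population. A subject must complete the assigned dose level or placebo and, in the words shared with protocol 8.1.4, "have sufficient data for evaluation of the primary endpoint (based on a blinded review of data prior to database lock"). The next sentence adds the exclusion: "Subjects who do not have at least 1 observation within 2 hours of" Tmax "for Drug Liking VAS will be excluded from the Completer population". Protocol 8.5 and SAP 9 make this the default population for all PD results.

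Four other places bear on what Tmax means here:

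- SAP Table 8-1 defines Tmax as a plasma quantity: "Time of maximum observed concentration; if it occurs at more than 1 timepoint", the first such time is taken. It applies to five analytes: "The PK parameters for mitragynine, 7-hydroxy-mitragynine, paynantheine, speciogynine, and speciociliatine are defined in" that table.
- SAP 4.3 keeps placebo out of the concentration analyses: "Participants who received only placebo will not be included in the PK population".
- SAP 9 gives the PD peak its own symbol, TEmax: "Time of maximum observed post-dose effect".
- SAP 9.3 nevertheless says that Emax, Tmax and TA_AUE "of key secondary PD endpoints, Overall Drug Liking, Take Drug Again, and High VAS will be summarized similarly by treatment".

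**The concern.** A rule that decides who enters the only population named for the PD analyses should be capable of being applied, and applied alike in both arms. Taken with the SAP's formal definition of Tmax, this one cannot be. Placebo subjects have no plasma peak, kratom subjects may have five, and using individual concentrations would sit badly with a review meant to be blinded. Taken as the time of peak liking, the rule seems to do nothing. Taken as an expected time, it lacks a value and an analyte.

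At stake is an Emax taken from a profile that is missing its peak. Such gaps are conceivable. Protocol 6.3 has testing aborted when an adverse event prevents timely completion and foresees subjects falling asleep, and protocol 1.3 links doses above 7 to 8 g with strong sedation. Groups are small: one exclusion removes 1 of 6 subjects at a dose level, or 1 of 10 in pooled placebo.

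**Working it through.** **Inputs.** There are five cohorts of 8, randomised 6:2 (SAP 3.1 and 3.4). Drug Liking is rated 13 times, at 0.25, 0.5, 1, 1.5, 2, 2.5, 3, 4, 6, 8, 10, 12 and 24 h (SAP Table 9-3). Post-dose PK samples fall at the same times plus 48 h (protocol Table 6-7). The plan states no numerical result for this rule, so there is no figure to reproduce.

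**Which reading does the text support?** SAP Table 2-1 lists Emax, TEmax and TA_AUE for High VAS. SAP 9.3 lists the same three quantities for High VAS but writes Tmax for the middle one. It does so for Overall Drug Liking and Take Drug Again as well. A rating scale has no plasma peak, so Tmax in SAP 9.3 can only be the time of peak effect. SAP 4.4 attaches Tmax to Drug Liking VAS in the same way.

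**Reading 1: time of peak Drug Liking.** The peak is itself one of the subject's scores, so its distance from the reference time is 0, which is within 2 h. Any subject with at least one score passes. An enumeration agrees: 2^13 − 1 = 8,191 non-empty patterns of available scores, with 3 random score sets each, give 24,573 cases and 0 exclusions. Only a subject with no Drug Liking score fails, and that subject has no Emax to analyse.

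**Reading 2: plasma Tmax.** Placebo subjects: 5 × 2 = 10, and 10/40 = 25% could not be assessed. For the other 30, the number of scheduled scores within 2 h (inclusive, nominal times) is:

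| Tmax (h) | 0.25 | 0.5 | 1 | 1.5 | 2 | 2.5 | 3 | 4 | 6 | 8 | 10 | 12 | 24 | 48 |
|---|---|---|---|---|---|---|---|---|---|---|---|---|---|---|
| Scores | 5 | 6 | 7 | 7 | 8 | 7 | 6 | 5 | 3 | 3 | 3 | 2 | 1 | 0 |

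Exclusion requires every score in the window to be missing. For a Tmax from 1 to 4 h that means 5 to 8 missing scores. With all 13 scores present, a subject fails only if the peak is the 48 h sample.

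**Reading 3: an expected Tmax.** No value is given, so a range is assumed. A subject missing 0.25 to 3 h is excluded at an assumed 0.5, 1 or 1.5 h and kept at 2 h or later. A subject with scores only at 0.25 to 1 h is kept at 0.5 to 3 h and excluded at 4 h or later. The value matters, but only for profiles as sparse as these.

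**Nominal or actual time?** Protocol Table 6-8 lets a draw move by 5 minutes between 4 and 12 h, and scores follow the draw and pupillometry. Suppose the peak is the 8 h draw. With both draws on time, the 10 h score comes 1 to 10 minutes after 10 h, so the gap is 2 h 1 min to 2 h 10 min and the score is outside. With the 8 h draw at 8 h 5 min, the 10 h draw at 9 h 55 min and the score at 9 h 56 min, the gap is 1 h 51 min and the score is inside. A score scheduled exactly 2 h from the peak can fall either way. This arises only under a plasma reading with actual times.

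**The case for a change.** The strongest case for a change runs as follows. If the clause is redundant, the plan has lost its only numerical test for membership of the PD population. What remains is a requirement for sufficient data with no threshold, and SAP 5.4 on missing data covers safety and PK only. SAP 5 describes its analyses as fixed in advance, yet the reference time or the threshold would be settled later. In groups of 6, one such decision is visible in the results.

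Part of this stands. The term is undefined, and sufficiency is left to judgement. But the judgement is made blind and before lock, so it cannot be steered by treatment. SAP 9 handles a similar decision, whether out-of-window assessments enter the time-point summaries, in the same way before unblinding. Other PD completeness rules are explicit: the time-averaged area over the curve is not computed if the first or last scheduled time is missing (SAP 9), and Bowdle composites and ARCI scales are not scored if an item is missing (SAP 9.2.2 and 9.2.4).

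The obvious remedies add little. Asking the sponsor for a nominal window without being able to say which one only moves the same judgement elsewhere, and it leaves sufficiency undefined. A second set of PD tables in all dosed subjects would largely repeat the first if few are excluded. Editing the protocol text would also require IRB approval under protocol 12.2.

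**Conclusion.** The wording is loose, but following the plan produces no wrong PD result. The likeliest meaning is the time of peak Drug Liking. The clause is then redundant and treats kratom and placebo alike. The plasma reading, which gives the figure of 10 placebo subjects in 40 who cannot be assessed, is hard to intend: SAP 4.4 expressly admits placebo completers, and SAP 9.3 pools placebo as the comparator for every dose. The reference to a primary endpoint in the same paragraph is also loose, since the study's primary endpoint is safety, but the context points to Drug Liking Emax.

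The expected effect is nil or small. This rests on three assumptions: analysts read Tmax here as SAP 9.3 uses it; the blinded review looks at whether the peak period was observed; and most of the 13 ratings are obtained from subjects confined for 48 h. The documents give no missing-data rate, so the number of subjects affected cannot be computed. PD is a secondary objective in a study that protocol 3.2 calls hypothesis-forming, no formal sample size was set, and the safety analysis is untouched. This is a gap that analysts fill sensibly at the blinded review, and no change is called for.

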## 5 DATA HANDLING AND PRESENTATION

All safety and statistical outputs will be generated using SAS software, version 9.4 or higher. The PK outputs will be generated using the same version of SAS.

All programs used to generate statistical analyses will be validated according to Altasciences' Standard Operating Procedures (SOPs).

The analyses described in this plan are considered a priori, in that they have been defined prior to database lock and/or prior to breaking the blind. Any analyses performed subsequent to database lock and/or breaking the blind will be considered post hoc and exploratory, and will be identified in the Clinical Study Report (CSR).

### 5.1 Safety Analysis Presentation

Adverse events and medical history will be classified using the Medical Dictionary for Regulatory Activities (MedDRA) terminology as defined in the study Data Management Plan (DMP).

Prior and concomitant medications will be coded with the World Health Organization Drug Dictionary (WHODrug) as defined in the study DMP.

In general, all safety summary tables will be presented for the safety population. Summaries for AEs will be presented by treatment (active dose levels and pooled placebo) and overall.

Summaries for other safety endpoints will be presented by treatment (active dose levels and pooled placebo).

In general, the data listings will include all subjects in the safety population up to the point of study completion or discontinuation; exceptions will be listings pertaining to a subset of subjects only (e.g., subjects with protocol deviations) or a subset of records/events (e.g., abnormal laboratory values). Limited data for those not included in the safety population, e.g., who failed screening, may be presented, as appropriate.

Categorical variables will be summarized using sample size (N), number of available data (n), and the percentage of available data (%) for each class. Continuous variables will be summarized using descriptive statistics, including N, n, arithmetic mean (mean), standard deviation (SD), minimum (min), median, and maximum (max).

The following general considerations may be applied:

- Study Day will be derived from the reference date (e.g., the day of the first dose of study drug) and date of event as:  
Study Day = (date of event – reference date) +1, if event is on or after the reference date;  
Study Day = date of event – reference date, if event is before the reference date.
- Duration will be calculated using the general formula: (end date - start date) +1.
- If the reported value of a clinical laboratory parameter cannot be used in a statistical summary table (e.g., a character string is reported for a parameter of the numerical type), a coded value may be appropriately determined and used in the statistical analyses. In general, a value below the lower limit of normal range such as ' $<10$ ' or ' $\leq 5$ ' will be treated as half of the lower limit, '5' or '2.5', respectively, and a value above the upper

limit of normal range such as ‘>100’ will be replaced with a number deemed scientifically reasonable, e.g., 101. However, the actual values as reported in the database will be presented in data listings.

- Unscheduled assessments will not be included in descriptive summary, except for baseline consideration. When assessments are repeated for a given timepoint or performed at unscheduled times, only the result which is the closest to the dosing time will be included in summary tables.

In general, summary statistics for raw variables (i.e., variables measured at the study site or central laboratory) will be displayed as follows:

- Minima and maxima will be displayed to the same number of decimal places as the raw data
- Means, medians, and quartiles (if presented) will be displayed to 1 additional decimal place
- Standard deviations will be displayed to 2 additional decimal places
- Percentages will be displayed to 1 decimal place; Percentages between 0 and 0.1 (exclusive) will be displayed as ‘<0.1’
- P-values will be displayed to 3 decimal places; P-values that are less than 0.001 will be displayed as ‘<0.001’

Derived variables (i.e., variables that are not measured by the study site but are calculated for analysis based on other measured variables) will be displayed with the same precision as the raw data, as appropriated, then follow the similar rules in presentation of summary statistics.

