**Table 10-1 Clinical Laboratory Assessments**

Clinical Laboratory Test Panel	Description
General biochemistry:	Alanine aminotransferase, albumin, alkaline phosphatase, anion gap, aspartate aminotransferase, bilirubin total, blood urea nitrogen (BUN), BUN/creatinine ratio, calcium, carbon dioxide, chloride, creatinine, (including eGFR calculated using the CKD-EPI equation), glucose, phosphorus, potassium, protein total, sodium, and uric acid
Lipid profile:	Total cholesterol, cholesterol high-density lipoprotein, cholesterol low-density lipoprotein and triglycerides
Endocrinology:	FSH a
Hematology:	White cell count with differential (absolute values of neutrophil, lymphocyte, monocyte, eosinophil, and basophil), red cell count, hemoglobin, hematocrit, mean corpuscular hemoglobin, mean corpuscular hemoglobin concentration, mean corpuscular volume, and platelet count, red cell distribution width
Serology:	HIV Ag/Ab Combo, Hepatitis B surface antigen and Hepatitis C virus
Urinalysis:	Color, clarity, specific gravity, pH, leukocyte, protein, glucose, ketones, bilirubin, blood, nitrite, urobilinogen. Microscopic examination will only be performed if the dipstick test is outside of the reference range for leukocyte, blood, nitrite or protein
Urine drug screen:	Amphetamines, barbiturates, benzodiazepines, cocaine, fentanyl, MDMA, opiates, oxycodone, phencyclidine and tetrahydrocannabinol
Pregnancy test:	Serum pregnancy test at Screening only and urine pregnancy test at all other scheduled days
Alcohol screen:	Urine alcohol test

Abbreviations: eGFR = estimated glomerular filtration rate; FSH = follicle-stimulating hormone; HIV = human immunodeficiency virus.

a. Performed for females in a postmenopausal state only.

The following listings will be presented:

- All laboratory values by category
- Out-of-range laboratory values
- Clinically significant laboratory values

For protocol-specified laboratory parameters, summary tables on observed and change from baseline values will be presented by treatment and visit for each category, including biochemistry (including lipid profile), hematology, and urinalysis (quantitative data only).

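### SAP 5.1's default of coding a low, text-form laboratory result at half its limit has no exception for scales that do not start at zero, such as urine specific gravity and pH

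*SAP*

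**What the plan says.** SAP 5.1 (Safety Analysis Presentation) introduces a list of conventions with "The following general considerations may be applied". One of them concerns laboratory results that arrive as text:

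- The trigger is "If the reported value of a clinical laboratory parameter cannot be used in a statistical summary table"; in that case "a coded value may be appropriately determined and used in the statistical analyses".
- On the low side, the convention says that in general a result such as `<10` or `≤5` "will be treated as half of the lower limit", which it works out as 5 and 2.5. The text ties the limit to the normal range, but the two examples halve the number inside the reported string. No parameter is exempted.
- On the high side, a result such as `>100` "will be replaced with a number deemed scientifically reasonable, e.g., 101".
- Listings keep the result as reported.

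SAP 10.2 then asks for tables of observed values and change from baseline, by treatment and visit, for biochemistry, hematology and the quantitative part of urinalysis. Table 10-1 gives the urinalysis panel as "Color, clarity, specific gravity, pH, leukocyte, protein, glucose, ketones" and further items. Under SAP 5.1 continuous variables are shown with mean, SD, minimum, median and maximum, by active dose level and pooled placebo.

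**The concern.** Half the limit is a reasonable stand-in for a concentration, which can lie anywhere between zero and the limit. It is not reasonable for a quantity whose possible values stop well above zero. Specific gravity is a ratio to water, so all urine values sit slightly above 1, and half of any such limit is about half the density of water. pH is a logarithmic scale on which half a low limit falls far outside the plausible range for urine.

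These two are the clearly numeric items in the urinalysis panel. If the laboratory reports low results for them as text and the default is followed, artificial values enter the mean, SD, minimum and change from baseline of groups of about 6. A dose level could then appear to differ from placebo only because one result was text. Laboratory tests are part of the primary safety endpoint, so the tables should not contain such figures, even though they are purely descriptive.

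**Working it through.** **Inputs from the documents.** Coding rule: limit divided by 2 (SAP 5.1). Active group: 6 per dose level (SAP 3.4). Pooled placebo: 2 per cohort × 5 cohorts = 10 (SAP Table 3-1).

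**Assumed inputs, not in the documents.** That specific gravity or pH is reported as `<x` or `≤x` at all; limits of 1.005 (range 1.001 to 1.005) and 5.0 (range 4.5 to 5.5); and the values of the other subjects.

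**1. The plan's own figures.** 10/2 = 5 and 5/2 = 2.5. Both SAP examples reproduce exactly.

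**2. Coded values.** Specific gravity: 1.005/2 = 0.5025 (0.5005 for a limit of 1.001). pH: 5.0/2 = 2.5 (2.25 to 2.75 for limits of 4.5 to 5.5).

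**3. Shift in the mean.** Compared with coding at the limit L, one coded value among n lowers the mean by (L/2)/n.

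- Specific gravity: 0.5025/6 = 0.084; with n = 10, 0.050.
- pH: 2.5/6 = 0.42; with n = 10, 0.25.

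**4. SD.** Let d be the distance from the coded value to the mean of the other n − 1 values, and S the sum of squares of those others about their own mean. Then SD² = [S + d²(n − 1)/n]/(n − 1), so the SD is at least d/√n.

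- Specific gravity, others 1.010, 1.015, 1.020, 1.025, 1.018 (mean 1.0176): d = 1.0176 − 0.5025 = 0.5151, and 0.5151/√6 = 0.210.
- pH, others 5.5, 6.0, 6.5, 7.0, 6.0 (mean 6.2): d = 3.7 and S = 1.30, so SD² = (1.30 + 13.69 × 5/6)/5 = 2.54 and SD = 1.59.

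| One low result | Coding | Mean | SD | Median | Minimum |
|---|---|---|---|---|---|
| Specific gravity, n = 6 | at limit | 1.0155 | 0.0072 | 1.0165 | 1.005 |
| | half | 0.932 | 0.210 | 1.0165 | 0.5025 |
| pH, n = 6 | at limit | 6.00 | 0.71 | 6.0 | 5.0 |
| | half | 5.58 | 1.59 | 6.0 | 2.5 |
| Specific gravity, n = 10 | at limit | 1.0163 | 0.0066 | 1.0165 | 1.005 |
| | half | 0.966 | 0.163 | 1.0165 | 0.5025 |
| pH, n = 10 | at limit | 6.10 | 0.66 | 6.0 | 5.0 |
| | half | 5.85 | 1.29 | 6.0 | 2.5 |

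The n = 10 rows repeat the same five values to make up the nine others.

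**5. Sensitivity to the assumed data.** A second specific gravity set (1.012, 1.018, 1.020, 1.015, 1.022 and one low result) gives an SD of 0.0062 coded at 1.005 and 0.210 coded at half. With the other five values simulated as normal and floored at the limit, the median ratio of the two SDs is 35 to 26 for specific gravity (assumed SD 0.004 to 0.008) and 3.0 to 2.1 for pH (assumed SD 0.3 to 0.8).

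**6. Change from baseline.** Suppose one reading is 1.010 and the other is `≤1.005`. If the text result is post-dose, the coded change is 0.5025 − 1.010 = −0.5075, against −0.005 when coded at the limit. If the text result is the baseline, the change is +0.5075. Either way the group mean change moves by 0.084. If both readings are text at the same limit, the change is zero under either coding.

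**The case against.** The strongest reply is that nothing obliges the statistician to print an impossible value. The conventions are permissive, the coded value is to be chosen appropriately, and halving applies only in general. That is right: a reader might infer that the SAP mandates these values, and it does not. What remains is that halving is the only concrete instruction for low results. A reasonableness test appears only on the high side, and SAP 5 treats as a priori only what is defined before database lock and/or unblinding. The exception is better written down than left to whoever programs the table.

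Second, the trigger is not in the documents. No section says that the laboratory reports specific gravity or pH as a limit, and 1.005 is an illustrative figure. This stands in full: if the laboratory reports plain numbers, the effect is zero.

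Third, several stronger readings are not supported.

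- A reader might take the `≤5` example in SAP 5.1 to be about pH. It names no analyte; only the number coincides.
- A reader might say that the artefact overwhelms pH as it does specific gravity. It does not: a shift of 0.42 against an SD of 0.71 is a distortion, while a shift of 0.084 against 0.0062 to 0.0072 exceeds 11 SDs.
- A reader might say that the tables become unreadable or that a safety signal would be missed. The median is also tabulated, a minimum of 0.5025 would expose the artefact, and SAP 10.2 lists all, out-of-range and clinically significant values. Under protocol 6.1.6 the investigator judges each abnormal result independently of the coding.
- A reader might want the `>x` rule changed too. It already gives a value next to the limit (100 becomes 101), and no harm from it can be shown.

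**Conclusion.** The concern holds as a conditional, minor one: the SAP has an unsafe default, not a certain error. If specific gravity or pH is reported as `<x` or `≤x`, and if the default is applied as written, one such result in a group of 6 gives an impossible specific gravity (SD up roughly 26- to 35-fold) or an implausible pH (SD up roughly 2- to 3-fold). Pooled placebo is affected less because it has 10 subjects.

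The distortion is confined to the mean, SD, minimum and change from baseline in descriptive safety tables. In the worked examples the median of observed values does not move at all. No hypothesis test, sample size or stopping rule depends on these figures: the stopping rules in protocol 4.3.2.1 rest on adverse events, on abnormalities judged in the individual subject and on compliance, not on group laboratory summaries.

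The result rests on three assumptions: that such text results occur, that their limits lie near those used here, and that the SAP counts specific gravity and pH as quantitative urinalysis.

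**What to change.** Amend the low-side convention in SAP 5.1 along these lines:

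> For urine specific gravity, pH and any other parameter whose scale does not start at zero, a result reported as `<x` or `≤x` is coded as x. For concentrations below a reporting or quantitation limit, half that limit is used.

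In the same bullet, refer to the reporting limit instead of the limit of the normal range, so that the wording agrees with the SAP's own examples, which halve the reported number. Leave the `>x` convention as it is. Coding at x brings the low side into line with that convention, which already stays close to the limit. The separate rule in SAP 8.2 for plasma concentrations is not touched.

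The cost is one or two sentences and a small programming change, best made before database lock. If no such text result ever occurs, the change has no effect on any table.
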